12.4. Analysis of the primary endpoint

The main objective of the study is to evaluate the incidence of post-COVID morbidity and characterize the complications profile in the cohort of patients who participated in the APLICOV-PC study.

The number and percentage of patients who develop complications related to persistent illness, as judged by a physician, during the period between the end of the APLICOV-PC proof of concept study and the end of this extension study by the patient, as well as the percentage of patients who present complications.

A description of the following endpoints will also be presented:

- Number and percentage of patients who required readmission to hospital and causes, since last visit of APLICOV-PC study until the end of this extension study.
- Need for oxygen therapy and duration of the same, since last visit of APLICOV-PC study until the end of this extension study.
- The maximum, minimum, Q1 and Q3, mean, median and standard deviation of the duration of the oxygen therapy will be provided.
- Number and percentage of patients who presented complications (see annex 5).
- Barthel Index [\[26\]](#). A description will be provided with the frequency and percentage of each dependency category according to the score obtained:
 - 0-20: Total dependency
 - 21-60: Severe dependency
 - 61-90: Moderate dependency
 - 91-99: Slight dependency
 - 100: Independence
- The maximum, minimum, Q1 and Q3, mean, median and standard deviation of the parameters related to pulmonary function will be provided: SaO₂, PAFI, CVF, FEV1, FEV1/CVF and diffusion test.
- The maximum, minimum, Q1 and Q3, mean, median and standard deviation of the results of the 6 minute walk test will be provided.
- A description will be provided with the frequency and percentage of each category of the mMRC scale.
- Number and percentage of patients with abnormalities in the chest X-ray, in patients who present pneumonia upon entry into the APLICOV-PC study, and description of the abnormalities.
- Number and percentage of patients who presented abnormalities $\geq G2$ in the analytical parameters.
- Number and percentage of patients who presented abnormalities in the ECG, and description of the abnormalities.
- Number and percentage of patients who presented abnormalities in the heart Ultrasound/MUGA in patients who suffered a relevant cardiac event during their participation in the APLICOV-PC study, and description of the abnormalities.

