6.2 Patients characteristics

Demographic and baseline data:

- Age (years)
- Gender (male/female)
- Ethnic group (Arab; Caucasian; Latin; Asian; Black; Other)
- Weight (kg)
- Height (cm)
- Body surface area (BSA) (m²)
- Body mass index (BMI) - calculated

In addition to all the basal characteristics used in APLICOV-PC if it necessary.

7 Analysis of the primary endpoint

The main objective of the study is to evaluate the incidence of post-COVID-19 morbidity and characterize the profile of complications in the cohort of patients who participated in the APLICOV-PC study.

The number and percentage of patients who develop complications related to persistent illness, according to the physician, during the period between the end of the APLICOV-PC proof of concept study and the completion of this extension study by the patient, as well as the percentage of patients who present complications will be detailed.

A description of the following endpoints will be presented:

- Number and percentage of patients who required readmission to hospital and causes, since last visit of APLICOV-PC study until the end of this extension study.
- Number and percentage of patients who needed oxygen therapy and duration of the same, since last visit of APLICOV-PC study until the end of this extension study.
- The maximum, minimum, Q1 and Q3, mean, median and standard deviation (Std) of the duration of the oxygen therapy.
- Number and percentage of patients who presented complications (defined in Annex 5 of the protocol).
- Barthel Index. A description with the frequency and percentage of each dependency category, according to the score obtained, will be provided:
 - 0-20: Total dependency
 - 21-60: Severe dependency
 - 61-90: Moderate dependency
 - 91-99: Slight dependency
 - 100: Independence
- The maximum, minimum, Q1 and Q3, mean, median and Std of the parameters related to pulmonary function will be provided: oxygen saturation (SaO₂), ratio of partial pressure arterial oxygen and fraction of inspired oxygen (PAFI), forced vital capacity (FVC), forced expiratory volume in 1 second (FEV1), FEV1/FVC and diffusion test.

- The maximum, minimum, Q1 and Q3, mean, median and Std of the results of the Six-minute walk test (6MWT).
- Frequency and percentage of each category of the modified Medical Research Council (mMRC) scale:
 - 0 (Dyspnea only after strenuous exercise)
 - 1 (Dyspnea occurring when hurrying on level ground or walking up a slight incline)

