 - 2 (Dyspnea resulting in walking more slowly than people of the same age on level ground or in stopping for breath when walking at own pace on level ground)
 - 3 (Dyspnea resulting in stopping for breath after walking about 100 meters or after a few minutes on level ground)
 - 4 (Dyspnea severe enough to prevent the person from leaving the house or occurring when dressing or undressing)
- In patients who present pneumonia upon entry into the APLICOV-PC study, number and percentage of patients with abnormalities in the chest X-ray and description of these abnormalities.
- Number and percentage of patients who presented abnormalities $\geq G2$ in the analytical parameters.
- Number and percentage of patients who presented abnormalities in the electrocardiogram (ECG) and description of these abnormalities.
- In patients suffering a relevant cardiac event during their participation in the APLICOV-PC study, number and percentage of patients who presented abnormalities in the heart Ultrasound/multigated acquisition scan (MUGA) and description of these abnormalities.
- Multivariate analysis to evaluate the relationship of the main covariates in the previous study (APLICOV-PC). More relevant exploratory covariates from the univariate analyses (p-value < 0.10) will be included in the multivariate analyses. The endpoints listed were correlated with the patients' basal characteristics, the degree of severity of the illness, comorbidities, the plitidepsin dosage, the viral load and the clinical evolution documented in the APLICOV-PC study.

8 Other analysis

- The maximum, minimum, Q1 and Q3, mean, median and Std of the vital signs will be provided: systolic blood pressure (SBP), diastolic blood pressure (DBP), heart rate (HR), temperature and respiratory rate.
- The maximum, minimum, Q1 and Q3, mean, median and Std of ECG parameters.
- Number and percentage of patients with abnormalities in the physical examination. The result will be listed.
- Number and percentage of patients with abnormalities in the neurological examination. The result will be listed.
- A description will be provided with the frequency and percentage of each category of the lung diffusion test:
 - Normal (between the 80 % and 120 % of the reference value)
 - Low (below the 80 % of the reference value)

- High (over the 120 % of the reference value)
- Number and percentage of patients who have been diagnosed of COVID-19 since the completion of APLICOV-PC study.

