Table 11.6 Pulmonary function assessment and diffusion test

Continuous endpoints	Dose Cohort																
	1.5					...					Total						
	N	Mean	Median	Range	Q1	*	N	Mean	Median	Range	Q1
Pulmonary function assessment																	
SaO ₂ (%)																	
PAO ₂ /FiO ₂																	
Spirometry																	
FVC (ml)																	
FEV1(ml)																	
FEV1 /FVC																	
Lung diffusion reference theoretical value																	

* Q3 and Std.

Table 11.7 Pulmonary function assessment

	Dose Cohort			
	1.5 mg N=X	2.0 mg N=X	2.5 mg N=X	Total N=X
	n (%)			
Spirometry				
Normal ($\geq 80\%$)				
Reduced ($< 80\%$)				
Lung diffusion testing				
Normal				
Low				
High				

Dyspnea assessment (mMRC)				
0				
1				
2				
3				
4				

Table 11.8 Barthel scale

	Dose Cohort			
	1.5 mg N=X	2.0 mg N=X	2.5 mg N=X	Total N=X
	n (%)			
Barthel scale				
Total dependency (0-20)				
Severe dependency (21-60)				
Moderate dependency (61-90)				
Slight dependency (91-99)				
Independence (100)				

Table 11.9 Six-minute walk test (I)

Continuous endpoints- 6MWT	Dose Cohort																	
	1.5						...						Total					
	N	Mean	Median	Range	Q1	...*	N	Mean	Median	Range	Q1	...*
Pre-TEST																		
Weight (Kg)																		
SBP (mmHg)																		
DBP (mmHg)																		
SpO ₂ (%)																		
Heart rate (bpm)																		
Post-TEST																		
SpO ₂ (%)																		
Heart rate (bpm)																		
Results																		

Continuous endpoints- 6MWT	Dose Cohort																		
	1.5							...							Total				
	N	Mean	Median	Range	Q1	...*	N	Mean	Median	Range	Q1	...*
	Total distance (m)																		
Expected distance (m)																			
Expected percentage (m)																			
Nº laps																			

* Q3 and Std.

Table 11.10.1 Six-minute walk test (II) by dose cohort

Categorical Endpoints (6MWT)	Dose Cohort			
	1.5 mg N=X	2.0 mg N=X	2.5 mg N=X	Total N=X
n (%)				
Pre-TEST				
Borg scale of dyspnea and fatigue at basal (1):				
Post-TEST				
Borg scale of dyspnea and fatigue after test (1):				
Results				
Stopped or paused				
Other symptoms at the end of the exercise (2)				

(1) 0 (None); 0.5 (Very, very slight); 1 (Very slight); 2 (Slight); 3 (Moderate); 4 (Somewhat severe); 5 (Severe); 6 (Severe); 7 (Very severe); 8 (Very severe); 9 (Very very severe); 10 (Maximal).

(2) Angina; Dizziness; Pain in hip, leg or calf; None

Table 11.10.2 Six-minute walk test (II) by severity of disease

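### SAP Table 11.6 summarises FVC and FEV1 only in raw millilitres, and its one diffusion row names the reference value rather than the patient's result

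*SAP*

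**What the plan says.** Protocol section 12.4 states that descriptive statistics of the "parameters related to pulmonary function will be provided" and lists "SaO₂, PAFI, CVF, FEV1, FEV1/CVF and diffusion test". SAP section 7 repeats the list, ending with "forced expiratory volume in 1 second (FEV1), FEV1/FVC and diffusion test". Neither passage gives a scale.

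The table shells supply the detail:

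- **Table 11.6** (continuous, by dose cohort and total) has six rows: SaO₂ in %, PaO₂/FiO₂, FVC in ml, FEV1 in ml, FEV1/FVC, and "Lung diffusion reference theoretical value". The diffusion row has no unit. There is no percent-predicted row for FVC or FEV1.
- **Table 11.7** (categorical) has a spirometry block, Normal at 80% or more and Reduced below 80%, and a block headed "Lung diffusion testing" with Normal, Low and High.
- **SAP section 8** defines the diffusion classes against the reference. The Low class, for instance, reads "Low (below the 80 % of the reference value"; Normal is 80% to 120% and High is above 120%. It gives no such definition for spirometry.
- **Table 11.9**, for the six-minute walk, carries expected-distance and expected-percentage rows beside the distance in metres.

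The last bullet of SAP section 7 and the end of protocol section 12.4 say that the listed endpoints are related to baseline characteristics, severity, comorbidities, plitidepsin dose, viral load and clinical course.

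**The concern.** A mean FVC in millilitres does not say whether a group is impaired. The same volume can be normal for one patient and reduced for another of different sex, height or age. With at most 42 patients over three dose cohorts, those characteristics will differ between cohorts by chance. A correlation of raw FVC or FEV1 with dose or severity would pick up the same mixture.

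The diffusion row raises a separate problem. A reference value is fixed by the patient's characteristics and carries no information about damage. A programmer who follows the label would produce a table that omits the promised result.

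The 80% cut for spirometry in Table 11.7 does not say whether it applies to FVC, FEV1 or their ratio, or what the percentage is of.

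These summaries matter because protocol section 5.1 names pulmonary fibrosis as the main sequela in severe disease and says that 87% of patients entered APLICOV-PC with moderate to severe illness.

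**Working it through.** The plan gives no figure of its own to reproduce here, so the check compares the text with the shells and adds an illustration.

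**1. Promise against delivery, diffusion.** Both endpoint lists promise continuous statistics of the diffusion test. Take four patients with the same reference value, set to 25 in arbitrary units:

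| % of reference | Measured value | Entry in Table 11.6, read literally | Class in Table 11.7 |
|---|---|---|---|
| 60 | 15.00 | 25 | Low |
| 79 | 19.75 | 25 | Low |
| 100 | 25.00 | 25 | Normal |
| 121 | 30.25 | 25 | High |

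The row in Table 11.6 is constant while the patients' results span three classes.

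**2. Could another output fill the gap?** SAP section 9 and the shells contain no listing of spirometry or diffusion, and ICH listing 16.2.6 is marked not applicable. As written, no measured or percent-of-reference diffusion value appears in any planned output.

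**3. Raw volumes.** Inputs: at most 42 patients (protocol section 12.2). Assumed: an even split, 42/3 = 14 per cohort; a sex gap in FVC of 1,000 ml (range 800 to 1,200); 10 men in one cohort and 7 in another; equal lung health.

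- Difference in mean FVC = (10 − 7)/14 × gap.
- Gap 800 ml: 171 ml. Gap 1,000 ml: 214 ml. Gap 1,200 ml: 257 ml.

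**4. Is such an imbalance unusual?** With a proportion p of men, the SD of the difference in male share between two cohorts is √(2p(1 − p)/14).

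- p = 0.50: 0.189. p = 0.67: 0.178.
- Multiplied by 800 to 1,200 ml, this is about 142 to 227 ml from sex alone.
- From the binomial distribution, two cohorts of 14 differ by at least 3 men with probability 0.34 at p = 0.50 and 0.31 at p = 0.67. For at least one pair among three cohorts, the probabilities are 0.61 and 0.57.

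The imbalance in step 3 would be ordinary.

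**5. Scale.** If mean predicted FVC is 3,500 to 4,500 ml (assumed), a true loss of 10% of predicted is 350 to 450 ml. Sex mix alone could therefore produce a substantial fraction of a difference that size, or hide it.

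**6. The 80% cut.** If FVC and FEV1 both fall to the same fraction k of predicted, FEV1/FVC = (k × predicted FEV1)/(k × predicted FVC), and k cancels. A cut on the ratio would not register the loss; a cut on percent predicted would. The shell does not say which is meant.

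**The case against.** The strongest reply is that Table 11.7 already covers most of this. It reports diffusion against the reference value and spirometry against an 80% cut, by dose cohort and in total. A reader might infer from Table 11.6 that patients' diffusion is not reported at all; Table 11.7 with SAP section 8 shows that this is wrong. A reader might also infer that lung function as a whole is reduced to raw volumes. That fails too: only two of the six rows in Table 11.6 are in millilitres, and the walk test has expected-value rows.

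The diffusion label may be loose wording for percentage of the reference. Other labels are careless: Table 11.9 has a row reading "Expected percentage (m", with metres as the unit of a percentage, and the laboratory table is headed as ECG endpoints. The documents do not settle what was intended.

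The plan is mainly descriptive, no test of FVC or FEV1 means between cohorts is specified, and Tables 10.4 and 10.5 would show an imbalance in sex, age or height. Protocol section 12.4 gives no scale, so millilitres do not contradict it.

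All of this stands and narrows the point. It does not remove it. Categories do not replace the promised continuous diffusion summary, an ambiguous label still needs correcting, a visible sex imbalance does not tell the reader how much of an FVC difference it explains, and the endpoints are to be correlated with dose and severity.

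**Conclusion.** The point holds for the continuous spirometry and diffusion rows of Table 11.6 and for the undefined 80% cut in Table 11.7. FVC and FEV1 in millilitres mix sex, height and age with impairment. The diffusion row, taken at its word, does not match SAP section 7 or protocol section 12.4.

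The effect is confined to the descriptive pulmonary summaries and the exploratory correlations. It would be wrong to infer that the main result is at risk: the primary endpoint is the incidence of complications, which does not use these rows.

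The 171 to 257 ml figure shows what could happen and does not predict what will. It rests on an assumed sex gap, an assumed 10 to 7 split and an assumed 14 patients per cohort. The documents give neither the sex distribution nor the cohort sizes.

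**What to change.** - **Table 11.6, spirometry:** keep FVC and FEV1 in ml and add each as a percentage of predicted. Use one reference equation named in the SAP, or the site-reported predicted values, and say which. Use the percent-predicted values in the correlations.
- **Table 11.6, diffusion:** replace the current row with the measured value as a percentage of reference, the scale already used in SAP section 8.
- **Table 11.7:** show the 80% cut in separate rows for FVC percent predicted and FEV1 percent predicted.

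No new patient procedures are needed. Age, sex, height and ethnic group are in SAP section 6.2, and spirometry and diffusion are in the protocol's evaluation calendar. The costs are choosing and justifying a reference equation, deriving a few variables and editing two shells. Before settling the wording, the sponsor should confirm that the database holds the numeric diffusion result or its percentage of reference. The documents imply this through the three classes but do not show the field.
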